8.1 Cabozantinib (NSC 761968)

8.1.1 Other Names

XL-184, Cabozantinib s-malate, EXEL-7184, EXEL-02977184, Cabometyx®

8.1.2 Classification

Receptor Tyrosine Kinases Inhibitor (RTK)

8.1.3 Mode of Action

XL184 inhibits multiple RTKs implicated in tumor growth, metastasis, and angiogenesis, and targets primarily MET and VEGFR2. Other targets are VEGFR3, RET, AXL, KIT, TIE-2, FLT-3, ROS1, and RON.

8.1.4 How Supplied

XL184 is supplied by Exelixis and distributed by the DCTD. XL184 will be provided in 20 mg tablets. The tablets are yellow film coated containing cabozantinib malate equivalent to 20 mg and 60 mg of cabozantinib. The 20 mg tablets have a round shape and they are packaged as 30 tablets per bottle.

XL184 should be dispensed in its original container; however, XL184 tablets can be dispensed in a pill cup with an expiration date not to exceed 24 hours. It can also be repackaged in a pharmacy dispensing bottle with expiration date not to exceed 7 days.

XL184 Tablet Components and Composition

Ingredient	Function	% w/w
Cabozantinib malate (25% drug load as cabozantinib)	Active Ingredient	31.7
Microcrystalline Cellulose (Avicel PH-102)	Filler	38.9
Lactose Anhydrous (60M)	Filler	19.4
Hydroxypropyl Cellulose (EXF)	Binder	3.0
Croscarmellose Sodium (Ac-Di-Sol)	Disintegrant	6.0
Colloidal Silicon Dioxide,	Glidant	0.3
Magnesium Stearate	Lubricant	0.75
Opadry Yellow Film Coating which includes:		
- HPMC 2910 / Hypromellose 6 cp		
- Titanium dioxide	Film Coating	4.00
- Triacetin		
- Iron Oxide Yellow		

Rev. Add4

8.1.5 Storage and Stability

Store intact bottles at controlled room temperature, 20° to 25°C (68°F to 77°F); temperature excursions are permitted between 15°C and 30°C (59°F to 86°F) [see USP Controlled Room Temperature].

If a storage temperature excursion is identified, promptly return XL 184 (Cabozantinib) to 20° to 25°C (68° to 77°F) and quarantine the supplies. Provide a detailed report of the excursion (including documentation of temperature monitoring and duration of the excursion) to [contact] for determination of suitability.

Commented [RE1]: Rev. Add4

Stability testing of the intact bottles is on-going. XL184 is stable up to 24 hours when dispensed in an open container such as a pill cup, and up to 7 days when dispensed in a closed container such as a pharmacy bottle other than the original container.

8.1.6 Dose Specifics

See Section 5 for dosing guidelines.

8.1.7 Route of Administration

Oral

8.1.8 Method of Administration

Take XL184 on an empty stomach; i.e., do not eat 2 hours before or 1 hour after each dose of XL184. Do not crush or chew. Do not take missed dose within 12 hours of the next dose.

8.1.9 Incompatibilities**CYP450 isozymes:**

In vitro, XL184 is a substrate of CYP3A4 and a weak substrate of CYP2C9. In healthy volunteers, XL184 AUC increased 38% with co-administration of ketoconazole, a strong inhibitor of CYP3A4, and decreased by 77% with a strong CYP3A4 inducer rifampin.

Therefore, avoid chronic use of strong CYP3A4 inducers such as rifampin, dexamethasone, phenytoin, carbamazepine, rifabutin, rifampicin, phenobarbital, and St. John's Wort while taking XL184. Avoid chronic use of strong CYP3A4 inhibitors such as ketoconazole, itraconazole, clarithromycin, indinavir, nefazodone, nelfinavir, and ritonavir. Use alternative medications.

NOTE: Use caution when discontinuing medication that is a strong inducer of CYP3A4 in patients who has been on a stable dose of XL184, as this could significantly increase the exposure to XL184.

XL184 is a noncompetitive inhibitor of CYP2C8 (Kiapp = 4.6 μ M), a mixed-type inhibitor of both CYP2C9 (Kiapp = 10.4 μ M) and CYP2C19 (Kiapp = 28.8 μ M), and a weak competitive inhibitor of CYP3A4 (estimated Kiapp = 282 μ M) in human liver microsomal (HLM). IC50 values >20 μ M were observed for CYP1A2, CYP2D6, and CYP3A4 isozymes. XL184 is an inducer of CYP1A1 mRNA in human hepatocyte incubations,

Avoid grapefruit/ grapefruit juice and Seville oranges while participating in this trial.

P-glycoprotein/ MRP2:

In vitro data indicate that XL184 is an inhibitor of P-glycoprotein transport activity (IC50 = 7.0 μ M). Co-administration of XL184 with a P-gp substrate may result in an increase in P-gp substrate plasma concentration. Therefore, use caution when administering XL-184 with drugs known to be P-gp substrates (e.g., fexofenadine, aliskiren, ambrisentan, digoxin, colchicine, maraviroc, posaconazole, tolvaptan, etc.).

XL184 is also a substrate of drug transporter MRP2, which may result in an increase plasma concentration of XL184 when administered with an inhibitor of MRP2. Use caution and monitor adverse events when administering XL184 with MRP2 inhibitors such as cyclosporine, delavirdine, efavirenz, emtricitabine.

Protein bound:

XL184 is highly protein bound (\geq 99.9%). Use caution when coadministering XL184 with medications that are highly protein-bound (e.g., diazepam, furosemide, dicloxacillin, and propranolol). Avoid administration of warfarin with XL184 as warfarin is highly protein-bound and has a very narrow therapeutic index.

Antacids, H2-blockers, PPIs:

Co-administration of gastric pH modifying drugs such as PPI, H2-blockers or antacids has no clinically-relevant effect on XL184 plasma PK in healthy volunteers; thus, concomitant use of these drugs with XL184 is allowed.

QTc prolongation:

Use caution when administering XL184 in patients with QT prolongation risk, a history of QT interval prolongation, or who are

receiving antiarrhythmic drugs. Concomitant use of strong CYP3A4 inhibitors should be avoided as it may increase XL184 plasma concentrations. Refer to the protocol for QTcF criteria.

Potential Food Effect

A high fat meal increased both XL184 Cmax and AUC values by 41% and 57%, respectively relative to fasted conditions; therefore, XL184 should be taken on an empty stomach (fasting is required 2 hours before and 1 hour after each XL184 dose).

8.1.10 Side Effects

See Section [5.3](#) for side effects.

8.1.11 Nursing/Patient Implications

Do not take grapefruit/ grapefruit juice or Seville oranges while participating in this trial. Inform physician and study healthcare team about current medications including over the counter drugs, herbals, or natural medicines. Refer to the protocol for management of adverse events.

8.2 Nivolumab (NSC 748726)

8.2.1 Other Names

BMS-936558, MDX1106

8.2.2 Classification

Anti-PD-1MAb

8.2.3 Mode of Action

Nivolumab targets the programmed death-1 (PD-1, cluster of differentiation 279 [CD279]) cell surface membrane receptor. PD-1 is a negative regulatory receptor expressed by activated T and B lymphocytes. Binding of PD-1 to its ligands, programmed death-ligand 1 (PD-L1) and 2 (PD-L2), results in the down-regulation of lymphocyte activation. Nivolumab inhibits the binding of PD-1 to PD-L1 and PD-L2. Inhibition of the interaction between PD-1 and its ligands promotes immune responses and antigen-specific T-cell responses to both foreign antigens as well as self-antigens.

Rev. Add4

8.2.4 Description

Nivolumab Injection is a clear to opalescent, colorless to pale yellow liquid; light (few) particulates may be present. The drug product is a sterile, nonpyrogenic, single-use, isotonic aqueous solution formulated in sodium citrate dihydrate, sodium chloride, mannitol, diethylenetriaminepentacetic acid (pentetic acid), polysorbate 80 (Tween® 80), and water for injection. Dilute solutions of hydrochloric acid and/or sodium hydroxide may be used for pH adjustment (pH 5.5-6.5).

Rev. Add4

8.2.5 Storage and Stability

Vials of Nivolumab injection must be stored at 2°-8°C (36°-46°F) and protected from light and freezing. The unopened vials can be stored at

room temperature (up to 25°C, 77°F) and room light for up to 48 hours.

If a storage temperature excursion is identified, promptly return Nivolumab to 2°C-8°C and quarantine the supplies. Provide a detailed report of the excursion (including documentation of temperature monitoring and duration of the excursion) to [contact] for determination of suitability.

Shelf-life surveillance of the intact vials is ongoing.

The administration of undiluted and diluted solutions of Nivolumab must be completed within 24 hours of preparation. If not used immediately, the infusion solution may be stored up to 24 hours in a refrigerator at 2°-8°C (36°-46°F) and a maximum of 8 hours of the total 24 hours can be at room temperature (20°-25°C, 68°-77°F) and room light. The maximum 8-hour period under room temperature and room light conditions includes the product administration period.

CAUTION: The single-use dosage form contains no antibacterial preservative or bacteriostatic agent. Therefore, it is advised that the product be discarded 8 hours after initial entry.

8.2.6 Dose Specifics

See Section 5 for dosing guidelines.

Rev. Add4

8.2.7 Preparation

Nivolumab injection can be infused undiluted (10 mg/mL) or diluted with 0.9% Sodium Chloride Injection, USP or 5% Dextrose. When the dose is based on patient weight (i.e., mg/kg), nivolumab injection can be infused undiluted or diluted to protein concentrations as low as 0.35 mg/mL. When the dose is fixed (eg, 240 mg, 360 mg, or 480 mg flat dose), nivolumab injection can be infused undiluted or diluted so as not to exceed a total infusion volume of 160 mL. For patients weighing less than 40 kilograms (kg), the total volume of infusion must not exceed 4 mL per kg of patient weight. During drug product preparation and handling, vigorous mixing or shaking is to be avoided.

Rev. Add4

8.2.8 Route of Administration

Intravenous infusion over 30 minutes. Do not administer as an IV push or bolus injection. Administer through a 0.2 micron to 1.2 micron pore size, low-protein binding (polyethersulfone membrane) in-line filter.

8.2.9 Incompatibilities

The indirect drug-drug interaction potential of nivolumab was assessed using systemic cytokine modulation data for cytokines known to modulate CYP enzymes. There were no meaningful changes in cytokines known to have indirect effects on CYP enzymes across all dose levels of nivolumab. This lack of cytokine modulation suggests that nivolumab has no or low potential for modulating CYP enzymes, thereby indicating a low risk of therapeutic protein-drug interaction.

Rev. Add4

8.2.10 Availability
Nivolumab is supplied by Bristol-Myers Squibb and distributed by the Pharmaceutical Management Branch, CTEP/DCTD/NCI as 100 mg vials (10 mg/mL) with a 0.7mL overfill. It is supplied in 10 mL type I flint glass vials, with fluoropolymer film-laminated rubber stoppers and aluminum seals.

8.2.11 Side Effects

See Section [5.3](#) for side effects

8.2.12 Nursing/Patient Implications

Women of childbearing potential (WOCBP) receiving nivolumab must continue contraception for a period of 5 months after the last dose of nivolumab. Men receiving nivolumab and who are sexually active with WOCBP must continue contraception for a period of 7 months after the last dose of nivolumab.

8.3 Ipilimumab (NSC 732442)

8.3.1 Other Names

Anti-CTLA-4 monoclonal antibody, MDX-010, Yervoy™

8.3.2 Classification

Human monoclonal antibody

8.3.3 Mode of Action

Ipilimumab is specific for the CTLA4 antigen expressed on a subset of activated T-cells. CTLA4 interaction with the B7 molecule, one of its ligands expressed on professional antigen presenting cells, can down-regulate T-cell response. Ipilimumab is, thought to act by blocking the interaction of CTLA4 with the B7 ligand, resulting in a blockade of the inhibitory effect of T-cell activation. The CTLA4/B7 creates the interaction.

Rev. Add4

8.3.4 Description

Ipilimumab is a fully human immunoglobulin (IgG₁κ) with two manufacturing processes – ongoing trials have been using substances manufactured using Process B. New clinical trials will be using ipilimumab that is manufactured by Process C. The Process C has been developed using a higher producing sub-clone of the current Master Cell Bank, and modified cell culture and purification steps.

8.3.5 Storage and Stability

Store intact vials refrigerated at (2° to 8° C), protected from light. Do not freeze.

Shelf-life surveillance of the intact vials is ongoing.

Solution as described above is stable up to 24 hours refrigerated at (2° to 8° C) or at room temperature/ room light.

CAUTION: Ipilimumab does not contain antibacterial preservatives. Use prepared IV solution immediately. Discard partially used vials.

	8.3.6	Dose Specifics
		
Dose adjustments do not need to be made every cycle for weight changes < 10% (but may if that is usual local practice). Dose must be adjusted if weight changes by 10% or more from the dosing weight. See Section 5.1.

Rev. Add4	8.3.7	
Preparation
 
Do not shake. Allow the vials to stand at room temperature for approximately 5 minutes prior to preparation of infusion. Ipilimumab is given undiluted or further diluted in 0.9% NaCl Injection, USP or 5% Dextrose Injection, USP in concentrations between 1 mg/mL and 4 mg/mL. Ipilimumab is stable in a polyvinyl chloride (PVC), non-PVC/non DEHP (di-(2-ethylhexyl) phthalate) IV bag or glass container up to 24 hours refrigerated at (2° to 8° C) or at room temperature/room light.
 
Recommended safety measures for preparation and handling include protective clothing, gloves, and safety cabinets.

Rev. Add4	8.3.8	
Route and Method of Administration
 
Intravenous infusion over 90 minutes. Do not administer ipilimumab as an IV push or bolus injection.
 
Can use a volumetric pump to infuse ipilimumab at the protocol-specific dose(s) and rate(s) via a PVC IV infusion set with an in-line, sterile, non-pyrogenic, low-protein-binding filter (0.2 micron to 1.2 micron).

Rev. Add4	8.3.9	
Availability
 
Bristol-Myers-Squibb (BMS) supplies ipilimumab to the DCTD/NCI. Ipilimumab injection, 200 mg/40 mL (5 mg/mL), is formulated as a clear to slightly opalescent, colorless to pale yellow, sterile, nonpyrogenic, single-use, isotonic aqueous solution that may contain particles.
 
Each vial is a Type I flint glass vial with gray butyl stoppers and sealed with aluminum seals.

	8.3.10	
Side Effects
 
See Section 5.3 for details.

	8.3.11	
Nursing/Patient Implications
 
Monitor patients for immune-related adverse events, e.g., rash/vitiligo, diarrhea/colitis, uveitis/episcleritis, hepatitis and hypothyroidism. If you suspect toxicity, refer to the protocol guidelines for ruling out other causes.

Rev. Add4		
Women of childbearing potential should be advised to continue contraception for 3 months following the last dose of ipilimumab
 
Post-marketing surveillance identified a fatal toxic epidermal necrolysis (TEN) event in a patient who received ipilimumab after experiencing a severe or life-threatening skin adverse reaction on a prior cancer immune stimulating therapy. Caution should be used

when considering the use of ipilimumab in a patient who has previously experienced a severe or life-threatening skin adverse reaction on a prior cancer immune stimulating therapy.

9. Statistical Considerations

9.1 Study Design and Objectives

Main study: This is a randomized phase II study comparing nivolumab (N) to the combination of nivolumab with cabozantinib (NC) and to the combination of nivolumab with cabozantinib and ipilimumab (NCI) in patients with 2nd line metastatic non-squamous non-small cell lung cancer. Prior therapy must have included one line of platinum-based chemotherapy, and must not have included any prior MET/PD-L1/PD-1 inhibitors. Patients must also not have any known activating mutations in EGFR, ALK, ROS1, RET or MET amplification/MET mutations, except for the targeted sub-arm below.

The primary objective of the trial is to determine whether combination therapy including nivolumab and cabozantinib or nivolumab and cabozantinib and ipilimumab extends progression-free survival (PFS) for this patient population as compared to nivolumab alone. Secondary objectives include estimation of overall survival, best objective response, and toxicity.

Targeted cohort sub-study: A separate arm (Arm T) will evaluate the efficacy of the combination of nivolumab and cabozantinib in patients with NSCLC tumor subtypes predicted to be sensitive to targeted agent cabozantinib (MET exon 14 mutations, MET amplification/other mutations, ROS1 rearrangement, RET rearrangement).

Rev. Add1
Rev. Add3

9.2 Study Endpoints

Main study: Progression-free survival (PFS) is defined as the time from randomization to documented disease progression (site review of imaging) or death from any cause, whichever occurs first. Patients who have not experienced an event of interest by the time of analysis will be censored at the date they are last known to be alive and progression-free. Overall survival is defined as the time from randomization to death from any cause, and patients who are thought to be alive at the time of final analysis will be censored at the last date of contact. Best objective response will be evaluated via RECIST1.1 criteria, as described in Section [6](#) of this protocol document. Toxicity will be determined using the CTCAE criteria.

Targeted therapy sub-study: This group will be evaluated by PFS, overall survival, best objective response rate, and toxicity as above.

Exploratory Imaging Correlative Study: For RECIST1.1 (central review) and irRC PFS is defined as the time from randomization to documented disease progression or death from any cause, whichever occurs first. For iRECIST, PFS is defined as the date of the time from randomization to documented disease progression (date of the documented iUPD that is followed by subsequent iCPD) or death from any cause, whichever occurs first.

For the imaging correlates, overall survival is defined as the time from randomization to death from any cause, and patients who are thought to be alive at the time of final analysis will be censored at the last date of contact. Best objective response will be evaluated for all three criteria performed by central review as defined in Section [6](#) of this protocol document.

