2.4 Imaging Endpoints

- 2.4.1 To describe time point tumor response assessment, overall best response and progression-free survival using the conventional RECIST1.1 criteria and the exploratory uni-dimensional immune response criteria (iRRC) and the iRECIST criteria with all measurements performed by the central review.
- 2.4.2 To compare RECIST1.1 imaging response assessment measurements (time point response assessment and overall best response) assess by site study personnel to those performed by central review.

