5.7 Duration of Therapy

Patients will receive protocol therapy unless:

- Patient declines further treatment to withdrawal of consent (Note that patients may decline further treatment without withdrawing consent for follow-up. The different levels of consent withdrawal should be documented in iMedidata/Rave)
- Disease progression by RECIST 1.1 criteria or clinically determined progression.

NOTE: Patients with disease progression by RECIST 1.1 may be continued on treatment as long as they are believed to still have potential clinical benefit from the study therapy and are otherwise medically stable. Generally this is most appropriate for patients with mild asymptomatic radiographic progression.

- Non-protocol anticancer therapies are administered (as outlined in Section [5.5](#), above)
- All study drugs have been held for more than 56 days, unless study chair approves resuming therapy after this point.
- Extraordinary Medical Circumstances: If at any time the constraints of this protocol are detrimental to the patient's health, protocol treatment should be discontinued. In this event submit forms according to the instructions in the EA5152 Forms Packet.

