- Measurements of iRECIST response will be performed as described by Seymour et al (Seymour ref) with time point and over all response assessments categorized as immune complete response (iCR), immune partial response (iPR), immune stable disease (iSD), immune unconfirmed progressive disease (iUPD) and confirmed progressive disease (iCPD).
- As per the iRECIST, all assessments of iUPD will be confirmed at subsequent reimaging (4-8 weeks later). Therefore, in patients with progressive disease, this criteria can only be performed on the patients that are maintained on therapy following evidence of progression on imaging with subsequent re-imaging acquired during the imaging window specified by the criteria. As such, this criteria will only be calculated on study patients with the available imaging.
- 6.2.3.1 Definitions
- Evaluable disease
- As detailed for RECIST1.1 in Section [6.1.1](#)
- Measureable disease
- As detailed for RECIST1.1 in Section [6.1.2](#) with the following differences. New target lesions are tabulated separately, measured with unidimensional measurements and summed separately. New lesions should be considered measureable or non-measureable by RECIST1.1 criteria principles (see Section [6.1.2](#)). Up to 2 new target lesions/organ (maximum 5 new visceral lesions) to be included in the sum of new lesions which are tabulated and summed separately at each time point
- 6.2.3.2 Assessment of target lesions by Immune Response Evaluation Criteria in Solid Tumor Criteria (iRECIST)
- Immune Complete Response (iCR), partial response (iPR) and stable disease (iSD)
- iCR, iPR and iSD are calculated in a manner identical to RECIST1.1
- Unconfirmed Progressive Disease (iUPD)
- iRECIST defines iUPD using RECIST1.1 principles for progression namely a requirement for at least a 20% increase in the sum of the diameters of target lesions, taking as reference the smallest sum on study (this includes the baseline sum if that is the smallest on study). In addition to the relative increase of 20%, the sum must also demonstrate an absolute increase of at least 5 mm.
- NOTE:** The appearance of one or more new lesions is also considered to meet the criteria for iUPD, Measurements for new lesions are tabulated separately (not included in the sum of baseline

target lesions) and considered separately at subsequent re-imaging (4-8 weeks later).

Confirmation of PD at subsequent re-imaging is necessary for iUPD to become iCPD.

Confirmed Progressive Disease (iCPD)

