Assessment for possible iCPD occurs at re-imaging 4-8 weeks following an assessment of iUPD which is done on the basis of observing either a further increase in size in the lesion category in which progression was first identified in (ie, target or non-target disease), or progression (defined by RECIST 1.1) in lesion categories that had not previously met RECIST 1.1 progression criteria. For the new lesion category, iUPD is considered confirmed if the sum of the new lesions increases by greater than 5 mm or new lesions appear.

NOTE: If iUPD is not confirmed by further progression of the tumor (see iCPD), however tumor shrinkage occurs and meets the criteria for iCR, iPR, iSD, then the bar is reset so that iUPD needs to occur again (compared with nadir values) and then be confirmed (by further growth) at the next assessment for iCPD to be assigned.

If no change in tumor size or extent from iUPD occurs, then the timepoint response would again be iUPD

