6.2.3.3 Assessment of non-target lesions by iRECIST

The iRECIST assessment of non-target lesions at each timepoint follows similar principles to evaluation of the iRECIST target lesions. iUPD (but not iCPD) can have been documented before iCR or when the criteria for neither CR nor PD have been met (referred to as non-iCPD/non-iUPD) and can be assigned several times, as long as iCPD was not confirmed. iUPD is defined by RECIST 1.1 criteria; however, iUPD can be assigned multiple times as long as iCPD is not confirmed at the next assessment. Progressive disease in the non-target lesion category is confirmed if subsequent imaging, done 4-8 weeks after iUPD, shows a further increase from iUPD. The criteria for iCPD are not judged to have been met if RECIST 1.1 criteria for complete response or non-iCR/non-iUPD are met after a previous iUPD. The status is reset (unlike RECIST 1.1) and iCR, or non-iCR/non-iUPD is assigned; if no change is detected, the timepoint response is iUPD.)

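### Exploratory imaging aim: Section 9.2 gives no iRECIST PFS rule for an iUPD with no later central read, so iRECIST PFS exceeds central RECIST 1.1 PFS even without pseudoprogression

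*Combined protocol and SAP*

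**What the plan says.** - **Event definitions (9.2).** Central RECIST 1.1 PFS and irRC PFS run from randomization to documented progression or death. For iRECIST the progression date is the "date of the documented iUPD that is followed by subsequent iCPD".
- **Trigger (6.2.3.2).** An iUPD uses the RECIST 1.1 thresholds: a 20% and 5 mm increase, or a new lesion. The scan that makes an iUPD is therefore also a RECIST 1.1 progression.
- **Confirmation (6.2.3).** Re-imaging is expected 4-8 weeks later, and "this criteria will only be calculated on study patients with the available imaging".
- **Scans read (6.2).** The imaging correlates use baseline and the first three follow-up time points.
- **Scans required (5.8; 7.1 footnote 11).** Imaging is every 8 weeks until progression.
- **After progression (5.7).** "Patients with disease progression by RECIST 1.1 may be continued on treatment", with the remark "Generally this is most appropriate for patients with mild asymptomatic radiographic progression".
- **Censoring (9.2).** The only PFS censoring sentence stands under the main study: patients without an event "will be censored at the date they are last known to be alive and progression-free".
- **Unchanged rescan.** 6.2.3.2 says "If no change in tumor size or extent from iUPD occurs, then the timepoint response would again be iUPD", and 6.2.3.3 says of non-target lesions "if no change is detected, the timepoint response is iUPD". Section 6.2.3.4, however, allows iSD or iPR to be assigned when new lesions have not regressed or non-target progression is unchanged, as long as iCPD is not met.
- **Purpose.** The aim in 2.4.1 is "To describe time point tumor response assessment, overall best response and progression-free survival" under the three criteria. Section 1.7 adds the hypothesis that PFS differs among them, and acknowledges that only patients kept on therapy past progression will have the re-imaging needed.

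**The concern.** Under 9.2 one scan is an immediate event for RECIST 1.1 and a conditional event for iRECIST. The condition is a later read that the plan often does not require, and for the third follow-up scan cannot supply. A patient with a real progression and no later read then counts as progressed under one criterion and not under the other, although nothing about the tumour differs.

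What is at stake is how the 1.7 comparison is read. A longer iRECIST PFS is what one would expect if pseudoprogression were being reclassified correctly. It is also what missing confirmatory reads produce by themselves. Without a stated rule, the analyst could drop such patients, leave them event-free until death, or censor them at the iUPD. These choices give different answers, and the choice could be made after the data are seen.

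**Working it through.** **Plan's own figures.** The imaging aim has no sample size or event count. The 9.4 inputs used here are consistent: ln 2/4 = 0.173 and ln 2/7.2 = 0.096 per month, as stated. For the main study, the Schoenfeld formula with hazard ratio 4/7.2, one-sided 0.10 and 89% power gives 73 events against 74 stated, and 74 events give 89.4% power. The point does not depend on these last two figures.

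**Inputs from the documents.** Median PFS of 4 months (Arm A) and 7.2 months (Arms B and C under the alternative); 43 eligible and treated patients per arm; scans at weeks 8, 16 and 24 (1.84, 3.68 and 5.52 months); reads end at the third scan.

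**Simplifying assumptions.** Exponential PFS, no death before progression, no pseudoprogression and, for steps 1-3, every rescan showing growth.

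**Step 1: when progression is first seen.** S(t) = exp(-rate x t).

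| | S at wk 8 | wk 16 | wk 24 | First seen on scan 3 | First seen on scans 1-3 |
|---|---|---|---|---|---|
| Median 4 | 0.727 | 0.529 | 0.384 | 0.144 | 0.616 |
| Median 7.2 | 0.838 | 0.702 | 0.588 | 0.114 | 0.412 |

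**Step 2: iUPDs that cannot be confirmed in these reads.** Arm A: 43 x 0.144 = 6.2 of 43 x 0.616 = 26.5. Arms B and C: 4.9 of 17.7 each. Total 6.2 + 4.9 + 4.9 = 16.0 of 26.5 + 17.7 + 17.7 = 61.9 (26%). With a 4-month median in all arms it is 18.6 of 79.4 (23%).

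**Step 3: week-24 PFS in Arm A if every week-8 and week-16 progressor is rescanned.** Central RECIST 1.1 gives 0.384. For iRECIST, with 0.471 progressed by week 16:
- unconfirmed iUPD dropped: 0.384/(0.384 + 0.471) = 0.449;
- not an event until death (9.2 as worded): 0.384 + 0.144 = 0.529;
- censored at the iUPD (Kaplan-Meier): (1 - 0.273)^2 = 0.529.

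The range is therefore 45-53% against 38%, caused only by the three-scan limit.

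**Step 4: incomplete rescanning.** Let p be the assumed share of week-8 and week-16 progressors with a later read, taken as random. Dropped: 0.384/(0.384 + 0.471p). Censored: (1 - 0.273p)^2. The until-death rule was simulated with an assumed median survival after progression of 5 to 8 months.

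| p | Dropped | Until death | Censored |
|---|---|---|---|
| 0.8 | 0.505 | 0.592-0.602 | 0.611 |
| 0.5 | 0.620 | 0.687-0.712 | 0.746 |
| 0.2 | 0.803 | 0.782-0.822 | 0.894 |

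The documents give no value for p.

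**Step 5: effect of the fix.** Counting every iUPD with no later read on its own date returns iRECIST PFS to 0.384 at any p, provided every rescan shows growth. If an assumed share u of rescans is unchanged and these are not counted, then with full rescanning and deaths ignored it is 0.384 + 0.471u: 0.431 at u = 0.1 and 0.479 at u = 0.2.

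**The case against.** The strongest reply is that confirmation is the purpose of iRECIST, so a difference from RECIST 1.1 is intended. That is right, and requiring confirmation is not the defect. The defect is that 9.2 does not say what happens when confirmation is impossible or was never sought.

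The plan is also not silent. Section 1.7 discloses the missing re-imaging and treats it as a limitation. Section 6.2.3 limits the calculation to patients with imaging, which points towards dropping the others. Section 9.3 assumes data are missing at random, without imputation. But none of these is an event rule. Dropping patients selects on a decision made after progression, one that 5.7 steers towards milder cases, and it still gives 45% against 38%.

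Sections 4.3 and 6.3.1 ask sites to submit all follow-up images, so later scans may be held centrally. Section 6.2 nevertheless confines the analysis to three follow-ups. Section 6.2.3 also refers to a published guideline, not available here, that may contain a convention; 9.2 writes its own PFS definition and does not refer to it.

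Three stronger readings are tempting and are not supported:
- A reader might infer that an unchanged rescan always remains iUPD and so never becomes an iRECIST event. Section 6.2.3.4 conflicts with that for new and non-target lesions, so the text leaves the status unsettled.
- A reader might infer that irRC has no confirmation rule. It has one, in 6.2.2 and 6.2.2.2; only the scan that dates the event is unclear.
- A reader might take the larger gaps in step 4 as expected. They rest on assumed rescan shares, and random rescanning is itself at odds with 5.7.

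**Conclusion.** The point holds, as a minor one confined to the exploratory, descriptive imaging aim. The rule in 9.2, combined with scanning only to progression and reading only three follow-ups, lengthens iRECIST PFS relative to central RECIST 1.1 with no pseudoprogression at all. The part that needs no assumed rescan share is 38% against 45-53% at week 24 in Arm A, and about 16 of 62 expected events that cannot be confirmed. Those figures assume exponential PFS at the 9.4 medians, no death before progression and, for the PFS comparison, growth on every rescan. The 129 patients behind the event count are the eligible and treated number, not the 144 to be randomized. The responses to review comments placed before the protocol report suspension for slow accrual, so actual counts would be smaller. It would be wrong to infer any effect on the primary PFS, which uses site review.

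**What to change.** In 9.2:
- Count an iUPD with no later central read as an iRECIST progression on the iUPD date, and keep the confirmed-only definition as a sensitivity analysis.
- Compare all three criteria in the same patients (everyone with central reads for this aim, not only those rescanned), with one cut-off at the third follow-up scan.
- Report by arm how many iUPDs had no later read.
- Reconcile 6.2.3.2 and 6.2.3.3 with 6.2.3.4 on an unchanged rescan, then state its consequence for PFS. Until that is done, step 5 shows that agreement with RECIST 1.1 in the absence of pseudoprogression is not guaranteed.
- State which scan dates an irPD event, given the confirmation required in 6.2.2, and apply the same no-later-read rule to it.

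The cost is wording in 9.2 and 6.2, with no new scans or reads. The downside is that true pseudoprogressors who were never rescanned count as progressed, which pulls iRECIST towards RECIST 1.1. The confirmed-only sensitivity analysis shows by how much.
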